8 SAFETY ANALYSES

All safety analyses will be carried out using the Safety Sample Set.

Descriptive statistics will be used to summarize all AEs and SAEs. Frequency and relative frequency will be used to present the number of subjects with AE, SAEs, and with each specific event. We will explore the expected and unexpected adverse events.

8.1.1 Safety monitoring

Adverse events will be tracked for the UA site at the follow up 14-30 day visit. All adverse events must be recorded on the AE tracking case report form (CRF). AEs related to study medication only will be tracked.

Each officer will be asked about potential study-related side effects for safety monitoring, i.e. they will be asked *“if they had any unpleasant experience, including an illness or other physical event, in the past 4 hours, whether they think it is study related or not?”* This will be followed by a question regarding their feeling of safety on the job, i.e. they will be asked *“if they feel safe partaking in required responsibilities associated with their job at this time or not?”*

Number and percentage of officers self-reporting potential study-related side effects or that report that they do not *feel safe partaking in required responsibilities associated with their job* will be reported to DSMB.

Cognitive assessments will be performed at baseline and within 24 hours following drug intake will be used to assess any side effects of ZNS on cognition. The assessments will be:

- a. Digit-symbol substitution test: Measures processing speed
- b. List learning task/RBANS: Measures memory function.
- c. Verbal fluency test (word finding task): Measures working memory, speech/language
- d. Stroop test: Measures executive functioning (vigilance, attention, inhibition).

Paired samples t-test will be used to explore the change from baseline to 24 hours following drug intake for each of the cognitive assessment instruments. The within subject change will be also compared to clinically meaningful differences for each of the test, to assess whether the observed change is clinically/practically important. Results of this analysis will be presented to DSMB.

The study team will monitor for adverse events on an ongoing basis. Once the team becomes aware of an adverse event, the AE will be reported according to institutional guidelines. Reporting requirements for University of Akron study team may be found in Section 1.1 of protocol. Reporting requirements for secondary site study teams participating in University of Akron-coordinated research may be found in Section 1.2 of protocol.

Early stopping rule related to serious adverse events: In the event of a serious adverse event, DSMB will evaluate the association of the serious adverse events with the study arm, break the blind if needed, and if found to be associated with treatment, DSMB will consider the study for revision or stopping.

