### **5.4 Follow-Up Assessments (Visits 3, 4 and 5)**

The follow-up assessments will occur after training and include the following tests or procedures:

1. Audiogram and DPOAEs to measure for TTS and auditory changes, as soon as possible after the training session. The exact time of testing following training operations will be documented. A clinical ear exam will be completed prior to the audiogram and DPOAEs. (follow-up visit 3 and 5).
2. Baseline environmental/ambient sound measurements will be recorded at the start of each test session, including the peak ambient noise level and the average noise level (follow-up visit 3 and 5).
3. Collection of blood for laboratory testing to include an electrolyte panel, BUN, Cr, ALT, and AST. This will occur within 12-24 hours following drug intake (follow-up visit 4).
4. Cognitive assessments within 24 hours following drug intake, including (follow-up visit 4):
  - a. Digit-symbol substitution test (processing speed)
  - b. Verbal fluency (working memory, speech/language)
  - c. Stroop (Executive function, inhibition)
  - d. List Learning task/RBANS (memory)

Additionally, after each officer is asked about potential study-related side effects for safety monitoring, they will be asked a question regarding their feeling of safety on the job, i.e. they will be asked *“if they feel safe partaking in required responsibilities associated with their job at this time or not?”*

5. Completion of LENS-Q 1-minute noise screening for noise exposure questionnaire (follow-up visit 5).
6. Audiogram, ECochG, DPOAE, and WIN testing 30 days (+/- 3 days) after each training session to assess for PTS and auditory changes, only if TTS is observed from #1 (visit 5).
7. Documentation of adverse events at all follow-up visits (5-30 minutes post, within 24 hours and at 30 day visit) (follow-up visit 3, 4 and 5).

Follow-up assessments will be planned at the stated time points; actual follow up times may vary due to patient logistics and compliance.

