## **8.0 REGULATORY AND REPORTING REQUIREMENTS**

The entities providing oversight of safety and compliance with the protocol require reporting as outlined below. Please refer to Appendix A for definitions and Appendix B for a grid of reporting timelines.

Adverse events will be tracked for the Akron site post dose within 30 minutes, 24 hours, and at 30 days. All adverse events must be recorded on the AE tracking case report form (CRF). AEs related to study medication only will be tracked.

Reporting requirements for Washington University study team may be found in Section 8.1. Reporting requirements for secondary site study teams participating in Washington University-coordinated research may be found in Section 8.2.

In the event of a Serious Adverse Event determined by the PI to necessitate the breaking of the blind, the intervention assignment will be revealed by the independent programmer to the medical staff doctor caring for the patient. In the event the statistician is unable to be reached in a timely manner, to assure the safety of the subject, the blind can be broken by [name] and information will be shared with the medical staff assuming care for the research subject.

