2.6 Schedule of Assessments and Procedures

The table below summarizes the calendar of study activities and assessments

	VISIT 1 Screening Assessment	VISIT 2 Baseline Assessment	Post-training		
			VISIT 3 Within 5-30 Minutes	VISIT 4 Within 24 Hours	VISIT 5 30 days (+/- 3 days)***
Informed Consent	X				
Demographic Info	X				
Current Meds	X				
Questionnaires	X				X
Cognitive Assessment		X		X	
Clinical ear exam	X	X	X		X
Audiogram	X	X	X		X
ECochG		X			X
DPOAE		X	X		X
WIN		X			X
Sound Measurements	X	X	X		X
Randomization			X*		

	VISIT 1 Screening Assessment	VISIT 2 Baseline Assessment	Post-training		
			VISIT 3 Within 5-30 Minutes	VISIT 4 Within 24 Hours	VISIT 5 30 days (+/- 3 days)***
Oral Dose* ZNS or Placebo			X*		
Blood draw**		X		X	
AE Assessment			X	X	X

* Dispensed after training if TTS is identified on audiogram 5-30 minutes after shooting.

** Blood draw: Electrolyte panel, BUN, Cr, ALT, and AST; DNA analysis and serum pregnancy test at baseline

***If TTS is seen from pure tones after each training session

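### The scripted side-effect question looks back only 4 hours but is placed at a visit up to 24 hours after the dose, so the self-report figure sent to the DSMB may miss short early effects

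*SAP*

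**What the plan says.** SAP 8.1.1 (Safety monitoring) gives the words of a side-effect question. Officers are asked "if they had any unpleasant experience, including an illness or other physical event, in the past 4 hours", whether or not they think it is related to the study. A second question follows, on whether they feel safe doing their job. The SAP gives neither a visit nor an hour for the pair. It then says what goes to the DSMB: "Number and percentage of officers self-reporting potential study-related side effects", together with those who report not feeling safe.

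Protocol 5.4 item 4 supplies the visit. Under the cognitive tests at Visit 4, due within 24 hours of the dose, it says that the job-safety question comes "after each officer is asked about potential study-related side effects for safety monitoring". The job-safety question has the same wording in both documents, so this is the same pair. Item 4 sets no earliest time. Item 3 of the same section says of the Visit 4 blood sample: "This will occur within 12-24 hours following drug intake (follow-up visit 4").

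Protocol 8.0 sets the general schedule: "Adverse events will be tracked for the Akron site post dose within 30 minutes, 24 hours, and at 30 days". SAP 8.1.1 instead says "Adverse events will be tracked for the UA site at the follow up 14-30 day visit". The SAP's own calendar (section 2.6) has no such visit. It shows adverse event assessment at Visits 3, 4 and 5, and the last of these is headed "VISIT 5 30 days (+/- 3 days").

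**The concern.** The look-back does not fit the visit. A question that reaches back 4 hours covers the time since dosing only if it is asked within about 4 hours of the dose, and Visit 4 may be as late as 24 hours after it. An effect that begins after the 30-minute check and has gone before the look-back starts is outside the question, and an officer who answers it literally would say no.

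The drug is given once, to working police officers. Somnolence, dizziness and ataxia are among the side effects listed in Protocol 7.1.7 and SAP 3.5. The DSMB could take a low self-report percentage as a sign of good tolerability when it partly reflects the width of the question's window. Efficacy is not involved.

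**Working it through.** The plan states no figure to reproduce, so the check is interval arithmetic.

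**Inputs**

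- Look-back L = 4 h (SAP 8.1.1).
- Earlier check at c = 0.5 h after the dose, taking the latest time that Protocol 8.0 allows.
- Asking time t, in hours after the dose: up to 24 h (Protocol 5.4 item 4), with no lower limit. The 12-24 h range belongs to the blood draw (item 3). It applies to the question only if both are done at the same sitting.

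**Formula**

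The question covers the time from t - L to t, and the earlier check covers the time up to c. The skipped time between them is max(0, t - L - c) = max(0, t - 4 - 0.5) = max(0, t - 4.5).

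| Asked at t (h after dose) | Skipped, 4-hour look-back (h) | Skipped, look-back to the dose (h) |
|---|---|---|
| up to 4.5 | 0 | 0 |
| 6 | 6 - 4.5 = 1.5 | 0 |
| 8 | 8 - 4.5 = 3.5 | 0 |
| 12 | 12 - 4.5 = 7.5 | 0 |
| 18 | 18 - 4.5 = 13.5 | 0 |
| 24 | 24 - 4.5 = 19.5 | 0 |

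**Sensitivity to the earlier check.** If that check falls at dosing (c = 0), the gap is t - 4: 12 - 4 = 8 h to 24 - 4 = 20 h over the blood-draw range. So 7.5 to 19.5 h is the smaller version of the range.

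**If 24 hours was meant.** With L = 24, the skipped time is max(0, t - 24 - 0.5) = 0 for every t up to 24 h.

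**Which effects are missed.** Only those that both start after the check and end before t - 4. An effect that starts in the gap and lasts into the final 4 hours is still reported. The documents give no onset or duration for the listed effects, so the number missed cannot be calculated.

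**The visit label.** SAP 2.6, the calendar in Protocol 9.0, Protocol 5.4 item 7 and Protocol 8.0 agree on an early check, one at about 24 hours and one at about 30 days. Only SAP 8.1.1 names a 14-30 day visit.

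**The case against.** The strongest reply is that capture does not depend on this question. Adverse events are documented at Visits 3, 4 and 5 with no stated look-back (Protocol 5.4 item 7 and both calendars). Participants are evaluated from the dose to 30 days (Protocol 6.0), and all events from the start of treatment go on the adverse event form (Protocol 11.1). SAP 8.1.1 adds continuous monitoring by the team, and SAP 8 summarises all events. The DSMB also receives a toxicity summary (Protocol 11.0) and the cognitive results. This stands, and it limits the point to one figure. One qualification is that Protocol 8.0 and SAP 8.1.1 also say that only drug-related events are tracked, whereas the scripted question asks regardless of attribution. General recording is therefore not an exact substitute for it, although drowsiness or dizziness attributed to the drug would still be recorded.

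Second, the asking hour is inferred. Neither document gives one, and a question asked by 4.5 hours leaves no gap. This also stands, and the size has to be stated as conditional.

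Third, the 4 hours may be a slip for 24, since the same SAP section uses 24 hours for the cognitive tests. The documents do not settle this. A slip would still need correcting, because a quoted script is likely to be read out as written.

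Fourth, the 14-30 day label looks like leftover text. The protocol's revision history records that adverse event timing was corrected from 2 weeks to 30 days. No schedule in either document has an officer seen on a different day because of it.

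**Conclusion.** The point holds in a limited form. As scripted, the question does not cover the whole time since dosing if it is asked later than 4.5 hours after the dose, and the self-report number and percentage may then undercount effects that come and go in the gap. The gap is t - 4.5 hours, or 7.5 to 19.5 hours if the question is asked at the Visit 4 blood draw. This rests on two assumptions: that the question is asked at Visit 4, as its place in Protocol 5.4 indicates, and that it is read out as written.

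A reader might infer that adverse events in those hours are lost to the trial, or that most of the first day goes unobserved whenever the question is asked. The documents support neither. General recording at Visits 3, 4 and 5 has no 4-hour limit. Hours that fall after the question has been asked cannot be charged to its look-back. Nor can one say how many effects are missed, because onset and duration are not given.

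One supplementary safety figure is affected. Efficacy, sample size and the stopping rule for serious events are not. The correction is still worth making because the DSMB sees the figure and the change costs almost nothing. The visit label is a clerical inconsistency and adds no weight.

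**What to change.** In SAP 8.1.1 and the matching interview script, replace *in the past 4 hours* with *since you took the study capsule* for the Visit 4 question. The skipped time before asking is then zero at any asking time. Hours after the question are left to general adverse event recording, as they are now.

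As a consistency edit only, replace the reference to a 14-30 day visit in SAP 8.1.1 with the Protocol 8.0 time points: within 30 minutes, at 24 hours and at 30 days after the dose.

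The cost is a wording change in two places and a recall period of up to 24 hours instead of 4, which is a small downside. No visit is added, and the sample size and efficacy analysis do not change.

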## **5.0 SCHEDULED ASSESSMENTS**

### **5.1 Screening (Visit 1) and Baseline (Visit 2) Assessments**

The screening assessment (Visit 1) will occur within 3 months of the first training session. The baseline assessment (Visit 2) will occur within one week of the first training following commencement of the study. These assessments will include the following tests or procedures:

1. Documentation of demographic information, including gender, age, allergies, and current medications (screening visit 1).
2. Clinical examination of the ears (screening and baseline visit 1 and 2).
3. Documentation of key clinical data such as confirmation of thresholds being  $\leq 25$  dB HL up to 4 kHz,  $\leq 30$  dB HL at 4 kHz, and  $\leq 45$  dB HL at 6 and 8 kHz, and the absence of any ear disorder (screening visit 1).
4. Blood draw for laboratory testing that include a serum pregnancy test\*, electrolyte panel, BUN, Cr, ALT, and AST and DNA analysis will be collected (baseline visit 2).

\*Women capable of becoming pregnant will be asked to have a pregnancy test before beginning this study. Women capable of becoming pregnant will be instructed to use effective birth control methods and not to become pregnant while participating in this study as there may be unknown risks to the unborn child. There may be long-term effects of the treatment being studied that could increase the risk of harm to an unborn child. The study team must be notified if the birth control method fails while on the study and/or if the participant becomes pregnant while participating in this research study.

5. Audiogram, ECochG, DPOAE, and WIN testing to document baseline measurements (baseline visit 2).

**Audiometry:** The audiogram will be performed to look for TTS and PTS. Earphones will be placed over the participant's ears and a series of tones at a soft volume will be played at varying frequencies. The participant indicates that they hear the tones by pressing a button. Thresholds will be measured from .025-16 kHz. If there is an absence of a threshold at the limits of the equipment, the threshold will be reported as equipment limits (in dB HL) + 10 dB HL. As with the DPOAE, all equipment and procedures are based on a clinically approved protocol. Each ear will be tested separately.

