2.5 Treatment Assignment and Blinding

The study will be “masked” or “blinded” in the sense that all the study subjects and the study team members will be blinded to the assignment in the study groups. Only the pharmacist who will prepare the study drug kits and the unblinded statistician will have access to the kit assignments. The Medical Monitor will be contacted. A copy of the randomization list with study ID assignments will be saved in a limited access folder on a secure network server at Pharm-Olam. The Medical Monitor will be contacted in emergent medical cases when knowing the treatments assignment is mandatory for clinical care of the study subject.

The data will be presented without having the treatment assignments of individual study subjects made known to study team members including the study PI. Table shells will be blinded. If DSMB members find any safety issues, they may request specific unblinded data. Table shells for DSMB (content and formats) will be agreed upon prior to start of study.

Subjects will receive one time dose of oral ZNS or matching placebo after training if TTS is identified on audiogram 5-30 minutes after shooting. Subjects will be instructed to take study drug without food. We will recommend that capsules be swallowed whole per the current approved labeling.

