8.2 Clinical Laboratory Tests

Biochemistry blood tests will be performed at screening for all subjects.

The following biochemistry laboratory parameters will be measured: Chloride, sodium, potassium, Carbon dioxide, Blood urea Nitrogen (BUN), creatinine, Alanine aminotransferase (ALT), Aspartate aminotransferase (AST).

Laboratory test results will be summarized descriptively by treatment group using Safety Analysis Sample.

All clinical laboratory results will be listed. Laboratory values that are outside the normal range will be flagged.

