Table 14.3.1.5	Summary of Related Treatment Emergent Adverse Events	Safety Sample Set
Table 14.3.1.6	Summary of TEAEs Leading to Study Drug Interruption	Safety Sample Set
Table 14.3.1.7	Summary of TEAEs Leading to Study Drug Withdrawn	Safety Sample Set
Table 14.3.2	Summary of Biochemistry Lab Results at Screening	Safety Sample Set

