12.2 Index of Proposed Listings

Listing Number	Listing Title	Sample Set
Listing 14.3.3.1	Overall Summary of Physical Examination of Ears Results at Screening	Safety Sample Set
Listing 16.1.1	Subject Enrollment and Disposition	All Subjects
Listing 16.1.2.1	Subject Inclusion and Exclusion Criteria	All Subjects
Listing 16.1.2.2	Protocol Deviations	All Subjects
Listing 16.1.3	Demographic Characteristics	All Subjects
Listing 16.1.4	Medical and Surgical History	Safety Sample Set
Listing 16.1.5	Hearing History and Occupation Exposure	Safety Sample Set
Listing 16.1.6	Concomitant Medications	Safety Sample Set
Listing 16.1.7	Study Drug Administration	Safety Sample Set
Listing 16.2.1	Audiogram Results on Hearing Thresholds	ITT Sample Set
Listing 16.2.2	Distortion Product Otoacoustic Emissions (DPOAE) Results	ITT Sample Set
Listing 16.2.3	Electrocochleography (ECochG) Results	ITT Sample Set
Listing 16.2.4	Word in Noise (WIN) Test Results	ITT Sample Set
Listing 16.2.5	LENS-Q Non-Military Occupational Noise Exposure Results	ITT Sample Set
Listing 16.2.6	LENS-Q Military Occupational Noise Exposure Results	ITT Sample Set
Listing 16.2.7	LENS-Q Non-Military Occupational Chemicals Exposure Results	ITT Sample Set
Listing 16.2.8	LENS-Q Military Occupational Chemicals Exposure Results	ITT Sample Set
Listing 16.2.9	LENS-Q Non-Occupational/Recreation Noise Exposure Results	ITT Sample Set

Listing Number	Listing Title	Sample Set
Listing 16.2.10	LENS-Q NON-Occupational/Recreation Chemicals Exposure Results	ITT Sample Set
Listing 16.2.11	Noise Exposure Questionnaire (NEQ) Responses	ITT Sample Set
Listing 16.2.12	Tinnitus Functional Index (TFI) Questionnaire Responses	ITT Sample Set
Listing 16.2.13	Audiologic and Medical History Questionnaire Responses	ITT Sample Set
Listing 16.2.14	Hearing Handicap Inventory for Adults (HHIA-A) Questionnaire Responses	ITT Sample Set
Listing 16.3.1.1	Serious Adverse Events	Safety Sample Set
Listing 16.3.1.2	Adverse Events Resulting in Death	Safety Sample Set
Listing 16.3.1.3	Treatment-emergent Adverse Events	Safety Sample Set
Listing 16.3.1.4	Treatment-emergent Adverse Events leading to Study Drug Interruption	Safety Sample Set
Listing 16.3.1.5	Treatment-emergent Adverse Events leading to Study Drug Withdrawn	Safety Sample Set
Listing 16.3.2.1	Clinical Laboratory Results at Screening: Biochemistry	Safety Sample Set
Listing 16.3.2.2	Pregnancy Test at Screening	Safety Sample Set

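### The SAP plans no ZNS–placebo comparison of cognitive change, and no titled table or listing covers the post-dose laboratory results

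*SAP*

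**What the plan says.** **Cognition.** SAP 8.1.1 schedules four tests (digit-symbol substitution, list learning/RBANS, verbal fluency, Stroop) at baseline and within 24 hours of drug intake, to be "used to assess any side effects of ZNS on cognition". The analysis is: "Paired samples t-test will be used to explore the change from baseline to 24 hours following drug intake". The SAP does not say whether this is run within each arm or on the arms combined. Within-subject change is also to be compared with clinically meaningful differences, but none is given. The results go to the DSMB. Protocol section 12 contains no cognitive analysis. On unblinding, SAP 2.5 states: "If DSMB members find any safety issues, they may request specific unblinded data".

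**Laboratory tests.** Protocol 5.1 and 5.4, the protocol calendar (section 9.0) and the SAP's own schedule (2.6) place blood draws at Visit 2 and Visit 4. The SAP 2.6 footnote describes the draw as "Electrolyte panel, BUN, Cr, ALT, and AST; DNA analysis and serum pregnancy test at baseline". SAP 8.2 says instead: "Biochemistry blood tests will be performed at screening for all subjects". Table 14.3.2 is titled "Summary of Biochemistry Lab Results at Screening" and Listing 16.3.2.1 is titled "Clinical Laboratory Results at Screening: Biochemistry". SAP 8.2 also promises a descriptive summary by treatment group, a listing of all results and flags for out-of-range values.

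**Adverse events.** SAP 8.1.1 places AE tracking at a 14–30 day visit, limits it to AEs related to study medication, and asks officers about the past 4 hours.

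**The concern.** A before–after change in the treated arm is the drug effect plus whatever else changed between the two sessions. Here the second session is a repeat of the same tests, within a day of dosing and after range training. Practice would push scores up; fatigue and noise exposure would push them down. A shared gain can hide a drug-related decline, and a shared decline can look like one. The trial has a concurrent randomised placebo arm that removes all of this, and the SAP does not use it here.

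The route to the DSMB adds to the problem. Table shells are blinded and the board may ask for unblinded data if it finds a safety issue. A cognitive effect may therefore first have to show itself in a result that the SAP does not tie to arm.

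On the laboratory side, both documents list metabolic acidosis as a possible serious effect of ZNS, and carbon dioxide is in the SAP 8.2 panel. The post-dose values are the ones that bear on that risk, and no titled table or listing covers them.

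Harm would not be invisible. AE and SAE tables remain, as does the question on whether officers feel safe doing their job. But the cognitive battery is the only objective measure of cognition in the trial.

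**Working it through.** **1. Is a between-arm cognitive comparison named anywhere?** The between-group ANCOVA in SAP 7.1.2 covers audiologic outcomes only. The control-versus-ZNS comparison in SAP 7.1.3 belongs to the pharmacogenetic analysis. SAP section 8 has none. The SAP section 12 indexes contain 30 tables, 32 listings and 7 figures, and none is for cognition.

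**2. What does this cost?** The plan states no cognitive power figure to reproduce. The inputs are:
- 66 officers per arm (SAP 2.7);
- assumed, not in the documents: two-sided 5% tests and effects in units of the SD of the change score; *g* is the gain shared by both arms and *h* the extra decline due to ZNS.

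The quantity computed is the chance of a significant decline, from the noncentral t distribution with these noncentrality parameters:
- paired, ZNS arm: (g − h)·√66, 65 df;
- paired, arms pooled: (g − h/2)/√(1 + h²/4)·√132, 131 df;
- between arms, on change: −h·√(66/2), 130 df.

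For g = 0.2 and h = 0.3 these are −0.81, +0.57 and −1.72. The pooled value has the wrong sign.

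| Shared gain g | Harm h | Paired, ZNS arm | Paired, pooled | Between arms |
|---|---|---|---|---|
| 0 | 0.3 | 67% | 39% | 40% |
| 0.1 | 0.3 | 36% | 8% | 40% |
| 0.2 | 0.3 | 12% | 0.6% | 40% |
| 0.3 | 0.3 | 2.5% | <0.1% | 40% |
| 0 | 0.5 | 98% | 79% | 81% |
| 0.2 | 0.5 | 67% | 8% | 81% |
| 0.3 | 0.5 | 36% | 0.6% | 81% |

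With no drug effect and a shared *decline* of 0.3, the chance of a false signal of decline is 67% (ZNS arm), 93% (pooled) and 2.5% (between arms).

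**3. Do paired p-values shown arm by arm solve it?** No. With no drug effect, each arm is significant with the same probability p, independently, so exactly one arm is significant with probability 2p(1 − p). At g = 0.2, p = 0.360 and 2 × 0.360 × 0.640 = 46%. At g = 0.3, p = 0.670 and 2 × 0.670 × 0.330 = 44%.

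**4. What would baseline adjustment give?** With baseline–follow-up correlation ρ, ANCOVA has residual SD √(1 − ρ²), against √(2(1 − ρ)) for the change score. The ratio is 0.87 at ρ = 0.5 and 0.95 at ρ = 0.8 (correlations assumed; 129 df). Power is 51% to 44% for harm 0.3 and 91% to 85% for harm 0.5.

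**5. Laboratory passages side by side.**

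| Source | Timing of biochemistry |
|---|---|
| Protocol 5.1, 5.4 and 9.0 | Visit 2, and Visit 4 (12–24 h after intake in 5.4) |
| SAP 2.6 schedule | Visit 2 and Visit 4; none at Visit 1 |
| SAP 8.2 | Screening |
| Table 14.3.2, Listing 16.3.2.1 | Screening |
| Figure 14.1.2 (QQ plot) | No visit named |

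Read literally, the outputs describe a visit with no scheduled draw, and the post-dose draw has no titled table or listing.

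**6. AE wording.** The single 14–30 day visit in SAP 8.1.1 conflicts with AE assessment at Visits 3, 4 and 5 (SAP 2.6, Protocol 5.4 and 9.0). Its restriction to related events, repeated in Protocol 8.0, conflicts with capture of all AEs (Protocol 11.1) and the summary of all AEs (SAP 8). A 4-hour look-back does not span the intervals between those visits.

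**The case against.** SAP 5.1 sets ZNS, placebo and overall columns as the default for tabular summaries and lists data by treatment group and visit. Means and SDs by arm would let a reader derive the difference, and pooling the arms becomes the less natural reading. This weakens the pooled column above. It does not supply a comparison: the default is a display rule, and no cognitive table is indexed for it to govern.

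The indexes are of proposed outputs, DSMB shells are to be agreed before the study starts (SAP 2.5), and the SAP may be modified at the DSMB's request (SAP 1). Absence from the index therefore does not prove that no cognitive output will be made. Nor does the SAP say that DSMB tables pool the arms; blinded shells could show masked arms. Both points stand, but the analysis that is written down remains within-subject.

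The magnitudes are assumed, the analysis is exploratory, and with no shared change the ZNS-arm paired test is more powerful than the proposed one (67% against 40%). All true. The difficulty is that its result depends on a shared change nobody knows. The gain from the repair is an unconfounded estimate with an interval, more than power.

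The laboratory point is a labelling conflict. SAP 8.2 promises that all results are listed and summarised by arm, so it is not evidence that post-dose values will be discarded. On AEs, SAP 8.1.1 also requires all events to be recorded and monitored on an ongoing basis, and the times in Protocol 8.0 agree with the calendar. The AE item is a separate wording matter.

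**Conclusion.** The concern holds and should be fixed; it does not touch the primary endpoint, alpha or sample size. The SAP assigns the cognitive tests to drug side effects but names no analysis that isolates a drug effect. For a 0.3 SD harm, the chance that a ZNS-arm paired test shows a decline falls from 67% to 2.5% as the shared gain goes from 0 to 0.3 SD, while the between-arm test stays at 40%. These figures rest on assumed effects and gains, 66 complete pairs per arm and two-sided 5% tests. The textual finding needs none of those assumptions. The between-arm interval will still be fairly wide: its half-width on the change score is about 1.978 × √(2/66) = 0.34 SD, so a non-significant result would not rule out a modest effect.

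The laboratory timing in SAP 8.2, Table 14.3.2 and Listing 16.3.2.1 contradicts the SAP's own schedule and the protocol, and leaves the Visit 4 results without a titled table or listing. The AE passages also need to be reconciled.

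**What to change.** - **SAP 8.1.1:** for each cognitive test, compare ZNS with placebo on the 24-hour score by ANCOVA adjusted for the baseline score, and report the difference with a 95% confidence interval. State the clinically meaningful threshold for each test, and report by arm the proportion of officers who decline by at least that much.
- **SAP 12:** add cognitive tables and listings.
- **SAP 8.2, Table 14.3.2 and Listing 16.3.2.1:** replace screening with baseline (Visit 2), post-dose (Visit 4), change, and out-of-range shifts by arm.
- **Adverse events:** reconcile the visit, relatedness and look-back wording in SAP 8.1.1, and the relatedness wording in Protocol 8.0, with Protocol 5.4, 9.0 and 11.1 and SAP 8.

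The cost is SAP text, a short wording correction in Protocol 8.0 if that passage is the one changed, one retitled table, one retitled listing and the new cognitive outputs. No extra officers, visits or tests are needed. Aligning the AE look-back may change one interview question.
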